#### **Measures**

Participants will receive a measure pack containing all measures, along with questions on medication use and adverse events.

#### **Idiographic Visual Analogue Scale**

The primary outcome will be assessed using a Visual Analogue Scale (VAS), a widely used measure

for tracking subjective experiences in clinical research (McCormack et al., 1988). Participants will rate their agreement with four daily statements on vertically presented 10 cm scales, with higher scores indicating stronger agreement. VAS items will be aligned with the research questions and reviewed for relevance by individuals with lived stroke experience via the university's Personal and Public Involvement (PPI) database.

The four VAS items will be:

1. Today, my mood is good (VAS\_mood)
2. Today, I feel able to accept the person I am/Today, I feel like I am adapting to life after my stroke (identity; VAS\_ID)
3. Today, I feel good about myself (self-esteem; VAS\_SE)
4. Today, I feel that I can use the wisdom of my life to help me deal with my current problems (VAS\_wisdom)

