## **Evaluation of the Wisdom Enhancement Timeline Approach for Post-Stroke Depression Using a Single-Case Experimental Design**

[name]1a, [name], [name]

**Date:** 26/03/2024

This study will aim to answer the question: *Does enhancing wisdom through the timeline technique improve mood in post-stroke depressed individuals?* Additionally, it will examine whether enhancing wisdom restores identity continuity and improves self-esteem.

It is hypothesised that wisdom will improve first, followed by gains in identity clarity or self-esteem, as structured self-reflection fosters agency and self-worth. Finally, mood regulation is expected to improve last, aligning with findings that emotional stabilisation follows meaning-making and self-affirmation rather than occurring simultaneously (Beaumont, 2009).

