### **Methods**

#### **Design**

A single-case experimental multiple-baseline design (MBD) will be adopted. Following Christ's (2007) recommendations, the study will pre-specify hypotheses, predetermine baseline durations, and randomise allocation via Random.org. Participants will be assigned to baseline durations of 2, 3, or 4 weeks, with non-concurrent intervention introduction to enhance flexibility. The independent variable will be the intervention, and the dependent variables will be mood, wisdom, identity, and self-esteem, measured repeatedly. Blinding will not be implemented due to feasibility constraints.

Although stability is generally recommended before intervention, Krasny-Pacini and Evans (2018) suggest that five baseline data points are sufficient to distinguish natural fluctuations from intervention effects. Replication will be built into the multiple-baseline design, with each participant serving as an independent test of the intervention's effects. Initially, a one-month follow-up review will be planned; however, this may be omitted if time does not permit.

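### The identity item prints two different statements under one score with no rule for their use, and neither measures the continuity or clarity named in the aim and hypothesis, so its results support only a conclusion about acceptance or adaptation

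*Combined protocol and SAP*

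**What the plan says.** The opening section puts the mood question first and then adds: "Additionally, it will examine whether enhancing wisdom restores identity continuity and improves self-esteem". Its hypothesis uses a different identity term: "It is hypothesised that wisdom will improve first, followed by gains in identity clarity or self-esteem", with mood improving last.

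The Design section states that "the dependent variables will be mood, wisdom, identity, and self-esteem, measured repeatedly". It does not define identity.

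Under Idiographic Visual Analogue Scale, the plan says: "Participants will rate their agreement with four daily statements on vertically presented 10 cm scales". Item 2, labelled identity (VAS_ID), reads "Today, I feel able to accept the person I am/Today, I feel like I am adapting to life after my stroke". Item 3, labelled self-esteem (VAS_SE), reads "Today, I feel good about myself". The same section says that the items will match the research questions and that people who have lived with stroke will review them for relevance.

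The only other outcome instrument, under Standardised Measure, is the PHQ-9, which is there for mood. The Analysis section applies Tau-U to the VAS ratings and adds piecewise regression with an estimated breakpoint.

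**The concern.** Two separate problems meet in one item.

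The first is what is rated. Someone can accept who they are without feeling that they are adapting, and the reverse. Two statements under one score need a rule for which of them the score reflects, and the plan gives none.

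The second is what the score stands for. The aim asks whether continuity is restored and the hypothesis predicts clarity. A person may come to accept being changed by the stroke, and so rate either statement higher, without feeling continuous with the person they were before.

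At stake is the identity claim. If the plan is followed exactly, a rise in VAS_ID would be reported as an answer to the continuity question although the item does not ask about continuity. The replication logic is also exposed. The study has three participants and treats each as a separate test, so the outcome has to be the same in all three.

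**Working it through.** The point turns on wording, and the plan states no figure for the identity outcome that could be reproduced. The check sets the sections side by side.

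1. **Construct against item.**
   - Opening section, aim: continuity of identity.
   - Opening section, hypothesis: clarity of identity.
   - Design: identity, undefined.
   - VAS item 2: self-acceptance / adaptation.

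   Neither half of item 2 refers to sameness with the pre-stroke self or to having a clear sense of who one is. The aim and the hypothesis also differ from each other.

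2. **Other sources of identity data.** The remaining VAS items cover mood, self-esteem and wisdom. The PHQ-9 covers mood. The measure pack adds only questions on medication and adverse events. Measures of continuity: 0. Measures of clarity: 0. Identity measures other than VAS_ID: 0.

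3. **Count of statements.** The text announces four statements and lists four items. Items 1, 3 and 4 hold one statement each and item 2 holds two: 1 + 2 + 1 + 1 = 5 printed. Either the slash joins two statements on one line, or it marks alternatives from which one is used.

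4. **Consequence under each reading.**
   - *Both rated on one line:* the item is double-barrelled, and one mark cannot show which statement it answers.
   - *One chosen:* the plan does not say who chooses, when, or whether the choice holds across phases. If it differs between participants, fewer than three of them replicate the same outcome. If it changes between baseline and intervention, any gap between the two statements enters the phase comparison as a level shift.

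   Under both readings step 1 stands.

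5. **Can a size be given?** Not from the documents. Suppose a participant averages the two statements, each with SD 1 and correlation r, with improvements of 1 and s. The standardised effect on the average is then d = [(1 + s)/2] / √[(1 + r)/2]. All these inputs are assumptions.
   - r = 0.5, s = 0: 0.5/0.866 = 0.58.
   - r = 0.5, s = 1: 1/0.866 = 1.15.
   - At r = 0.5, d = 1 when s = 2(0.866) − 1 = 0.73.
   - s = 0, with r from 0 to 0.9: d runs from 0.71 to 0.51.

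   Averaging can weaken or strengthen the apparent effect, depending on values nobody has. No single magnitude is offered.

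**The case against.** The strongest reply is that the slash marks alternative wordings, one per participant. The heading calls the scale idiographic and the text counts four statements, and both fit that reading. It may be right. If so, the item is not double-barrelled for any one person, and what is missing is a selection rule held fixed across phases.

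A second reply is that acceptance and adaptation are reasonable proxies. Table 1 places identity change in session 2 and self-acceptance in session 3, so the items follow the therapy's content. That supports measuring them. It does not turn them into measures of continuity or clarity.

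A third is that the items are to match the research questions and be reviewed by people with experience of stroke. This mitigates the problem, but the review is for relevance, and the printed wording of item 2 does not match the identity question.

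A reader might go further than the documents allow in four ways:

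- *That the trial cannot address identity at all.* Acceptance and adaptation are related to identity, so a narrower conclusion remains available.
- *That the whole predicted sequence depends on VAS_ID.* The middle step is "followed by gains in identity clarity or self-esteem", so it can be met through VAS_SE alone. Only the identity branch depends on item 2.
- *That VAS_ID duplicates VAS_SE.* The self-acceptance half sits close to item 3 in content, but the documents do not show how far the two overlap, and the adaptation half is different.
- *That pairing the statements must dilute a true effect.* The arithmetic above shows that the direction is not determined.

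**Conclusion.** The point holds in a limited form. Item 2 puts two different statements under one score without a rule for their use. Neither directly measures the continuity in the aim or the clarity in the hypothesis, and nothing else in the plan measures identity. The identity results can support only a conclusion about self-acceptance or adaptation, and only if it is known which of the two was rated. If wordings differ between participants or days, the three replications do not share one identity outcome.

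The mismatch of construct rests on the printed wording alone and holds under either reading of the slash. The loss of replication is conditional on the wording actually varying, which the plan neither states nor rules out. Identity is an additional question, and the mood question is unaffected. The change is worth making before data collection because the analysis cannot recover which statement a rating referred to.

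**What to change.** Before the first baseline rating:

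1. Use one statement for VAS_ID, identical for every participant on every day. If both existing statements are kept, give each its own 10 cm line and name one in advance as VAS_ID.
2. Then bring the wording and the claim into line, in one of two ways:
   - choose a single construct, continuity or clarity, use that term in both the aim and the hypothesis, word the VAS_ID statement to ask about it, and check the wording in the lived-experience review already planned; or
   - restate the identity aim and hypothesis as self-acceptance or adaptation, whichever the retained statement measures.

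The cost is one reworded line, or one extra line per day, in the measure pack, and possibly a minor ethics amendment. The second route instead costs a narrower identity claim. A reworded statement would still be a single unvalidated item, so the identity result should be reported with that limit.

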### **Standardised Measure**

The Patient Health Questionnaire (PHQ-9; Kroenke et al., 2001) will assess pre–post clinical mood changes. This nine-item tool (scoring 0–27) reliably detects clinically significant depression and is validated for PSD screening across diverse demographic groups with minimal somatic symptom confounding (Blake et al., 2025; Katzan et al., 2021).

### **Intervention**

Laidlaw's (2021) Wisdom Enhancement Timeline will be delivered in six structured, manualised sessions (Table 1), guiding participants through autobiographical reflection using a visual timeline of meaningful life events. To ensure accessibility and relevance, the manual will be reviewed for comprehensibility by individuals with lived stroke experience via the university's PPI panel.

Fidelity will be monitored through recorded sessions and assessed using the Revised Cognitive Therapy Scale (CTS-R; James et al., 2001), which evaluates therapeutic quality and adherence to the CBT framework. Ratings will be conducted by a Clinical Psychologist supervising the author, ensuring competence and consistency in intervention delivery.

**Table 1. Overview of the Intervention Sessions and Key Objectives**

Session Focus	Key Activities
1 Information gathering, rapport-building and goal setting	Assess individual difficulties, set client-focused goals
2 Psychoeducation on stroke impact and introduction to the timeline	Discuss changes in identity, mood and self-esteem; introduce the concept of wisdom and the timeline intervention
3 Reflected on timeline events	Reflect on complex life events, promote resilience, meaning-making, self-compassion, and self-acceptance
4–5 Active change methods	Explore past coping strategies and identify significance in events of regret

Session Focus	Key Activities
6 Review and consolidation	Reflect on learning, review new perspectives

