#### **Participants**

Three participants will be recruited, meeting SCED standards (Epstein et al., 2021; Kratochwill et al., 2013) through local stroke services. Inclusion criteria will require adults with post-stroke depression (PSD) who can provide informed consent and engage in therapy. Exclusion criteria will include severe cognitive or mental health impairments, medical instability, substance dependency, concurrent psychological treatment, participation in clinical trials, or newly prescribed psychotropic medication that has not yet stabilised. Participants who start psychotropic medication during the trial will remain eligible, as SCED analysis can account for medication-related changes.

NHS clinical teams will identify eligible participants, seeking permission for the researcher to contact them, while the author will conduct eligibility assessments and deliver the intervention. After the baseline phase, participants will attend six weekly sessions, either in person at a hospital or online via video conference.

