### **Analysis**

Both single-case visual and statistical techniques will be used following best practices (Harrington & Velicer, 2015; Manolov & Moeyaert, 2017). Visual analysis will assess phase variability using a  $\pm 25\%$  stability envelope (Lane & Gast, 2014). Higher percentages will indicate greater stability, and lower percentages will reflect greater variability.

To assess whether VAS ratings during the intervention phase are higher than baseline, Tau-U (Parker et al., 2011) will be implemented. It will account for baseline trends, effect sizes, and phase non-overlap. Resistant to autocorrelation, Tau-U provides strong statistical power in small datasets (Parker et al., 2014). Interpretations will follow Vannest and Ninci's (2015) guidelines, with baseline corrections applied as needed to prevent inflated effect sizes.

Piecewise regression (Center et al., 1985) will complement Tau-U findings by quantifying change over time within each phase. Level and slope changes will be examined, estimating the breakpoint for outcome improvements. This approach will model level shifts and gradual trends while considering data variability and abrupt changes (Tate & Perdices, 2018).

To address autocorrelation, lag-1 autocorrelation will be assessed, and if detected, Generalised Least Squares (GLS) regression with an AR(1) structure will be applied (Somer et al., 2022).

Reliable change in PHQ-9 will be measured via the Reliable Change Index (RCI; Jacobson & Truax, 1991), with Cronbach's  $\alpha = 0.79$  (De Man-Van Ginkel et al., 2012) and a stroke sample SD of 5.1 (Strong et al., 2021). Clinically Significant Change (CSC) will not be determined due to limited non-clinical-normative data for stroke populations. Given concerns about the comparability of PHQ-9 scores between stroke and non-stroke populations (Blake et al., 2025), data from other populations will not be considered. Instead, a cut-off of 10 will be applied to approximate clinically meaningful change, based on validated studies (De Man-Van Ginkel et al., 2012; Negeri et al., 2021; Williams et al., 2005).

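### The main Tau-U pools preparatory and timeline sessions, so it is diluted if mood responds only to timeline work and cannot tell that response from an early contact effect

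*Combined protocol and SAP*

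**What the plan says.** The aims section asks "Does enhancing wisdom through the timeline technique improve mood in post-stroke depressed individuals". It expects wisdom to improve first, identity or self-esteem next, and mood last.

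The Design section sets the baselines: "Participants will be assigned to baseline durations of 2, 3, or 4 weeks, with non-concurrent intervention introduction to enhance flexibility". Under Participants, treatment follows directly: "After the baseline phase, participants will attend six weekly sessions, either in person at a hospital or online via video conference". The visual analogue ratings are daily: "Participants will rate their agreement with four daily statements on vertically presented 10 cm scales".

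Table 1 describes session 1 as "Information gathering, rapport-building and goal setting". Session 2 is "Psychoeducation on stroke impact and introduction to the timeline", and its listed activities include "introduce the concept of wisdom and the timeline intervention". Reflection on timeline events appears first at session 3. The Intervention section nevertheless gives all six sessions the single name of the Wisdom Enhancement Timeline.

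The Analysis section applies Tau-U "To assess whether VAS ratings during the intervention phase are higher than baseline". It describes no lag and no separate treatment of the early sessions. It also plans piecewise regression of level and slope with an estimated breakpoint. It does not say whether that breakpoint is fixed or free, or how its date will be read against the session schedule.

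**The concern.** The question names a technique, while the main test covers everything delivered after baseline. This can mislead in two ways, under opposite conditions.

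- **Timeline work is what helps.** The first one or two weeks of the phase carry no effect but are counted as treated. Tau shrinks and power falls. Mood, which the plan expects to move last, is the outcome most exposed.
- **Starting regular contact with a therapist is what helps.** Ratings rise from session 1, and Tau is as large as for an immediate timeline effect, and larger than for a delayed one.

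Staggered baselines guard against history and maturation. They do not guard against contact, which starts with the intervention in every participant. There is no contact-only phase and no blinding. At stake is whether an answer given in terms of the timeline technique is supported by the contrast that produced it.

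**Working it through.** The documents give no power, effect-size or Tau figure on this point, so there is none to reproduce.

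**Inputs from the documents.** Baselines of 2, 3 or 4 weeks, that is 14, 21 or 28 daily ratings if complete; six weekly sessions; session content from Table 1.

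**Assumptions.** Phase length T is 42 days (six full weeks) or 35 days (session 1 to session 6). Delay k before any effect is 7 days (only session 1 lacks timeline content) or 14 days (effect starts with reflection at session 3). The effect is a step of 1 within-phase SD, with lag-1 autocorrelation 0.3, no baseline trend, complete daily data and a one-sided 5% test.

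**Step 1: dilution.** With no effect before day k and a step afterwards, expected full-phase Tau = ((T - k)/T) × Tau of the affected days.

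| Delay | T = 42 | T = 35 |
|---|---|---|
| 7 days | 35/42 = 83% | 28/35 = 80% |
| 14 days | 28/42 = 67% | 21/35 = 60% |

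**Step 2: Tau for a 1 SD step.** For normal ratings, Tau of affected days = 2Φ(1/√2) - 1 = 2(0.760) - 1 = 0.52. Over 42 days the full-phase value is 0.83 × 0.52 = 0.43 (7-day delay) or 0.67 × 0.52 = 0.35 (14-day delay).

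**Step 3: power per participant.** Simulated AR(1) series, T = 42, with critical values taken from the simulated null so that the test holds its 5% level under autocorrelation:

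| Contrast and onset | 14-day baseline | 28-day baseline |
|---|---|---|
| Full phase, onset after 7 days | about 0.60 | about 0.79 |
| Full phase, onset after 14 days | about 0.40 | about 0.60 |
| Baseline v session 3 onwards, either delay | about 0.70 | about 0.85 |

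The later-start contrast costs little if onset is in fact immediate: power goes from about 0.75 to 0.69 (14-day baseline) or from 0.91 to 0.86 (28-day).

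**Step 4: contact effect.** A 1 SD rise from session 1 caused only by contact gives full-phase Tau of about 0.52, the same as an immediate timeline effect of that size.

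**Step 5: what the planned breakpoint could add.** The model is not fully specified, so a single free step change fitted by least squares stood in for it. With independent errors, a 1 SD step delayed 14 days was placed at median day 14, with quartiles about days 12-16. At 0.5 SD the median was still about day 14, but the quartiles widened to about days 4-20.

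**Step 6: can a split at session 3 isolate the timeline?** A gradual non-specific rise from session 1 to 1.5 SD by day 42 gives Tau of about 0.40 between sessions 1-2 and sessions 3-6, significant in about half of series. Its Tau for baseline versus session 3 onwards is 0.52, the value a true 1 SD timeline step from session 3 would give. So it cannot.

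**The case against.** The strongest reply is that the intervention is the package. The protocol makes it the independent variable, gives the manualised six sessions one name, and can reasonably count assessment, goal setting and psychoeducation as treatment. For that estimand, using every day of the phase is consistent. This stands, and it is why the main Tau-U should stay. What remains is that the aims ask about the technique.

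Three stronger readings are tempting, and the documents do not support them.

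- A reader might infer that baseline versus intervention is the only contrast planned. It is not: the piecewise regression with an estimated breakpoint bears directly on when improvement starts. The gap is narrower: its form is unspecified, its timing is not linked to session content, and Step 5 suggests it is imprecise for modest effects.
- A reader might infer that two full weeks cannot carry a timeline effect. Session 2 introduces both wisdom and the timeline, so only the first week is clearly without such content. A range of 7 to 14 days is fair, and the 14-day figures are its upper end.
- A reader might infer that improvement after session 3 could be credited to the timeline. Therapist contact continues through sessions 3-6, and Step 6 shows that gradual non-specific improvement can imitate that pattern.

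It is also fair to say that dilution and false credit cannot both be the full story for one participant. They are alternatives, and full-phase Tau alone does not show which applies.

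**Conclusion.** The concern holds in a limited form. Full-phase Tau-U is a sound test of the six-session package but a weak one for the question as worded. If mood responds only once timeline work begins, Tau keeps 60-83% of its undiluted value, depending on delay and phase length. Under the stated assumptions, power with a 14-day baseline is about 0.40-0.60 instead of about 0.70. If early contact is what helps, the same statistic does not reveal it.

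The retained fractions follow from the session schedule and the step-effect assumption. The power values also rest on the assumed effect size, autocorrelation, complete data, phase length and test level, none of which the documents give; they illustrate scale and are not forecasts. This is worth correcting before the data are seen, but it does not invalidate the design.

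**What to change.** - Keep baseline versus the full phase as the main Tau-U, and state that it estimates the effect of the six-session package. Define the phase boundaries in days.
- Pre-specify, for VAS_mood, a secondary Tau-U of baseline versus session 3 onwards, using actual session dates.
- Report sessions 1-2 versus session 3 onwards descriptively, without a test-based claim.
- Add a fixed second break at session 3 to the piecewise/GLS model, with session 2 as a sensitivity analysis. State whether the estimated breakpoint is free.
- State conclusions for the package. Say in advance that improvement starting before session 3 does not support a timeline-specific effect, and that improvement starting after it is consistent with one but does not prove it, because contact continues.

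The cost is a few extra secondary results from daily ratings already planned, with no added burden on participants. The sessions 1-2 segment has only about 14 days, so anything estimated from it will be imprecise.
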